8.1.2 Supportive and sensitivity analyses of the primary efficacy variable

The primary efficacy analysis will be repeated in the subgroup of subjects with at least 1 documented AU flare within 12 months prior to Baseline.

The AU flares as reported by the investigators, without programmatically correcting for the 3 month interval between 2 flares, will be analyzed in addition to the primary efficacy variable of protocol-defined AU flares at least 3 months apart.

The primary analysis will be repeated using the pre-study period as 96 weeks (672 days) prior to start of study medication for counting flares and as the offset, instead of 24 months. The on-study period will be the same as that used for the primary analysis.

In addition, the analysis for the full 2 years before and after study medication will be provided. The pre-study period will be the 2 years (730 days) prior to start of study medication, which will be used for counting flares and as the offset. The on-study period will be determined for whose episodes of AU flares for which the start date of flare is on or after the start date of study

medication and up to and including the SFU visit or date of last administration of study medication + 70 days.

An analysis for the first 48 weeks will also be produced. The period for pre-study will be the 12 months (365 days) prior to start of study medication, which will be used for counting flares and as the offset. An episode of AU flares will be considered on-study, if the start date of flare is on or after the start date of study medication and up to and including the Week 48 visit or discontinuation visit if prior to Week 48. The exact date of the Week 48 or discontinuation visit will be used for each subject. This analysis will also be repeated using 48 weeks (336 days) as the pre-study period for counting flares and as offset, but keeping the on-study period of 48 weeks the same (i.e. using the exact date of the Week 48 or discontinuation visit).

The primary efficacy analysis will be repeated in the subgroup of subjects excluding those with any pre-study flares with completely missing end dates in the 2 years prior to baseline. Subjects will be excluded if any of the flares that started within the 2 years prior to baseline have completely missing end dates (i.e. no day, month or year)

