6.1 Inclusion criteria

To be eligible to participate in this study, all of the following criteria must be met:

- 1. An Institutional Review Board (IRB)/Independent Ethics Committee (IEC) approved written Informed Consent form is signed and dated by the subject.
- 2. Subject is considered reliable and capable of adhering to the protocol (eg, able to understand and complete diaries), visit schedule, or medication intake according to the judgment of the Investigator.
- 3. Subject is at least 18 years old at the Screening Visit.
- 4. Female subjects must be either postmenopausal for at least 1 year, surgically incapable of childbearing, or effectively practicing an acceptable method of contraception (including oral/parenteral/implantable hormonal contraceptives, intrauterine device or barrier and spermicide or contraception methods that are considered as at least as safe for contraception). Abstinence only is not an acceptable method. Subjects must agree to use adequate contraception during the study and for at least 5 months (in accordance with the Summary of Product Characteristics [SPC]) after the last dose of study treatment. Male subjects must agree to ensure that they or their female partner(s) use adequate contraception during the study and for at least 5 months (in accordance with the SPC), after the subject receives their last dose of study treatment.
- 5. Subjects must have a documented diagnosis of adult-onset axSpA with at least 3 months' symptom duration and meet the ASAS criteria (according to Appendix 16.2).

6a. Subjects must have active disease at Screening as defined by

- BASDAI score > 4
- Spinal pain ≥ 4 on a 0 to 10 NRS (from BASDAI item 2)
- Nr-axSpA subjects must either have CRP > upper limit of normal (ULN) and/or current evidence of sacroiliitis on MRI (no confirmation by central reading) as defined by ASAS criteria

- AS subjects must have evidence of sacroiliitis on x-ray meeting the mNY classification criteria according to the Investigator
- 7. Subjects must have a documented history of AU diagnosed by an ophthalmologist and
- 8. Subjects must be HLA-B27 positive (if known prior to Screening, no additional testing is to be performed; if unknown, testing is to be performed at Screening and checked at Baseline).

 9. Subjects must 1

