2.2.1.2 Secondary efficacy variables

The following secondary efficacy variables will be assessed at Week 48 and Week 96:

- Number of AU flares per 100 patient-years in subjects with active axSpA and a history of AU
- Number of AU flares per 100 patient-years in subjects with active axSpA and at least 1 AU episode within 12 months prior Baseline
- Change from Baseline in Ankylosing Spondylitis Disease Activity Score (ASDAS)
- Change from Baseline in Bath Ankylosing Spondylitis Disease Activity Index (BASDAI)
- Assessment of ASAS 20, 40, 5/6, and partial remission (PR) response rates
- Change from Baseline in tender and swollen joint count (44 joint count); Physician's Global Assessment of Disease Activity (PhGADA).
- Change from Baseline in the respective components of the ASAS response criteria, assessed by:
 - Patient's Global Assessment of Disease Activity (PtGADA)
 - Pain assessment (total spinal pain Numerical Rating Scale [NRS])
 - Function (represented by Bath Ankylosing Spondylitis Functional Index [BASFI])
 - Inflammation (the mean of the BASDAI questions 5 and 6 concerning [REDACTED])

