8.1.1 Derivations of primary efficacy variable

The primary efficacy variable is the number of distinct episodes of AU flares in the Treatment Period. Per protocol, a flare is considered a new episode if a gap of at least 3 months occurs between 2 flares. If AU flare episodes as reported by the investigator occur less than 3 months

(90 days) apart in the same eye, these will be programmatically corrected, such that a new AU flare within 3 months (90 days) after the end of the previous AU flare in the same eye will be considered as pertaining to the same AU episode. These flares will then be counted as one episode. Otherwise, if the time interval between 2 consecutive AU flares is greater than 3 months (90 days), or a separate eye is affected, the AU flares will be considered as separate episodes.

Pre-study and on-study AU flare episodes will be counted. An episode of AU flares is considered as pre-study, if the start date of flare is before the start date of study medication and if start date of flare occurs within the 24 months (730 days) prior to the start of study medication. For the interim analysis, an episode of AU flares is considered as pre-study if the flare occurs within 48 weeks (336 days) prior to the start of study medication.

For the Week 96 (primary) analysis, an episode of AU flares is considered on-study, if the start date of flare is on or after the start date of study medication and the start date of the flare occurs up to and including the last visit in the treatment period, i.e. Week 96 or discontinuation visit.

Pre-study and on-study flares of the same eye will be combined if the time interval between the end of pre-study flare and the start of subsequent on-study flare is less than 3 months (90 days). The resulting flare episode will be considered as pre-study flare episode.

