The log-time offset in the Poisson model will consist of the length of pre-study and on-study reporting periods in days. As the documentation of pre-study episodes is extended to up to 2 years prior to Baseline, the pre-study period length for offset is 730 days for each subject, unless the date of first uveitis flare is within 2 years of baseline, in which case the pre-study period length will be from date of first uveitis flare until baseline. The on-study period length for offset is the time in days from start of study medication until last visit, i.e. Week 96 or discontinuation visit. For the interim analysis, an offset of 336 days will be used for the pre-study period or time since first uveitis flare if shorter than 336 days, and the time in days from start of study medication until week 48 visit (taken as 336 days) or early termination visit (taken as 14 days after the last treatment) where applicable will be used for the on-study period.

Disease duration of axSpA, which will be included in the Poisson model as a factor, is calculated as defined in Section 6.2, and is categorized into <2 years and ≥ 2 years.

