8.2.1 Number of AU flares per 100 patient-years

The number of AU flares per 100 patient-years in subjects with active axSpA and a history of AU will be calculated and the corresponding 95% confidence interval for both pre-study and on-study periods. Similarly, the number of AU flares per 100 patient-years in subjects with active axSpA and at least 1 AU episode within 12 months prior Baseline, and the corresponding 95% confidence interval will be presented. This variable is also supportive of primary efficacy analysis.

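### The subgroup with a flare in the last 12 months is compared with a pre-study window that contains the qualifying flare, so with no drug effect its rate ratio is still expected to fall below 1, by an uncertain amount

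*SAP*

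**What the plan says.** Protocol 12.3.1 and SAP 8.1.2 say the primary analysis will be "repeated in the subgroup of subjects with at least 1 documented AU flare within 12 months prior to Baseline". The question is the first-listed secondary objective (Protocol 3.2, SAP 2.1.2).

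SAP 8.1.1 counts a flare as pre-study "if start date of flare occurs within the 24 months (730 days) prior to the start of study medication", with an offset of 730 days, or less if the first uveitis flare is more recent. It notes that "the documentation of pre-study episodes is extended to up to 2 years prior to Baseline". A shorter window is set as well: "For the interim analysis, an episode of AU flares is considered as pre-study if the flare occurs within 48 weeks (336 days" before the start of study medication.

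SAP 8.2.1 plans flare rates per 100 patient-years for the pre-study and on-study periods, and similarly for subjects with "at least 1 AU episode within 12 months prior Baseline, and the corresponding 95% confidence interval will be presented". SAP 2.2.1.2 fixes the timing: "The following secondary efficacy variables will be assessed at Week 48 and Week 96".

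The other analyses in SAP 8.1.2 change the window length (672, 730, 365 or 336 days), drop the 90-day merging, or exclude subjects with missing flare end dates. None removes the selection year. SAP 3.1 and SAP 8 call p-values outside the primary analysis nominal and non-confirmatory.

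**The concern.** Subjects enter this subgroup because they flared in a particular year, and that year is then part of their own comparator. The before count is conditioned to be at least one; the after count is not. A fall from before to after is expected even from an inert treatment. The planned ratio mixes any drug effect with this selection effect, and the subgroup rates in SAP 8.2.1 carry the same asymmetry. A reader of the secondary objective would see a reduction, perhaps with a small nominal p-value, and could not tell how much of it was built in.

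**Working it through.** **The plan's own figure.** Signorini formula, two equal groups, rates 0.292 and 0.146 per year, 1.5 years, 2-sided alpha 0.049, power 80%: N = [1.969·√4 + 0.842·√6]² / (1.5 × 0.292 × (ln 0.5)²) = 171.0 in total, 85.5 per group, rounded up to 86. This matches SAP 2.4. The documents give no figure for the subgroup.

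**Inputs.** Selection year and 730-day window: SAP 8.1.2 and 8.1.1. Rate 0.292 per year: SAP 2.4, a planning value obtained by assuming that CZP halves the rate. Rates of 1.0, 2.0 and 3.0 per year and gamma between-subject variance k of 0 to 4 are assumptions. Also assumed: a constant rate within each subject, no drug effect, the full 730-day offset, no 90-day merging, and no further selection on flares through inclusion criterion 7.

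**Formulas.** For mean rate λ, the chance of no flare in the selection year is P0 = (1+kλ)^(-1/k), or exp(-λ) if k = 0.
- Expected rate in the selection year among members: s = λ/(1-P0).
- Expected rate in any other year among members: o = λ[1 - P0/(1+kλ)]/(1-P0), or λ if k = 0.
- Ratio with no drug effect: 2o/(s+o) for 24 months, o/s for a window inside the selection year.

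Example, λ = 1.0, k = 1: P0 = 0.5, s = 2.0, o = (1 - 0.25)/0.5 = 1.5, ratio = 3.0/3.5 = 0.857.

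**Expected ratio with no drug effect, 24-month window.**

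| Rate per year | k=0 | k=1 | k=2 | k=4 |
|---|---|---|---|---|
| 0.292 | 0.404 | 0.572 | 0.665 | 0.765 |
| 1.0 | 0.775 | 0.857 | 0.894 | 0.928 |
| 2.0 | 0.927 | 0.941 | 0.953 | 0.967 |
| 3.0 | 0.974 | 0.968 | 0.972 | 0.979 |

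At 0.292 per year a true ratio of 0.5 would appear as 0.5 × (0.404 to 0.765), about 0.20 to 0.38.

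**336-day window.** A flare on days 337-365 before Baseline qualifies but is not counted. The bias stays, because the expected rate in any part of the selection year is s. The ratio is o/s: 0.25-0.62 at 0.292 per year and 0.63-0.87 at 1.0.

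**Nominal significance.** Simulation of 86 subjects (4,000 trials per setting, no effect, no merging, robust standard errors, period term only) gave p<0.05 in favour of CZP in 91%, 57% and 42% of trials at 0.292 per year for k = 0, 1, 2, and in 58%, 29% and 18% at 1.0. In all 86 unselected subjects it was 2-3%.

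**A comparator outside the selection year.** Days -730 to -366 cannot contain the qualifying flare. With complete dates and unmerged flares, the simulated median ratio with no effect was 1.00-1.02, with 3-4% false positives in that direction (nominal 2.5%).

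Year-only start dates disturb this. SAP 4.2 moves them to 1 January, or to the start of the pre-study period if they share its calendar year. Take a Baseline on 1 July of year Y. A year-only flare from Y-1 goes to 1 January Y-1 and one from Y-2 goes to day -730. Both land in days -730 to -366, even if they truly fell in the selection year or before day -730. With a share p of year-only dates, averaged over Baseline dates:
- imputed, flares before day -730 on record: two calendar years of such flares land in one, so 1/(1+p) = 0.91 (p = 10%), 0.83 (20%);
- imputed, earlier flares not on record: on average 1.5 years land, so 1/(1+0.5p) = 0.95, 0.91;
- left out of selection and count: 1/(1-p) = 1.11, 1.25.

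Simulation over rates of 0.292-2.0 and k = 0-4 agrees: imputed, about 0.90-0.96 at 10% and 0.83-0.91 at 20%.

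**The case against.** The strongest reply is that the analysis is declared non-confirmatory and its p-values nominal. That is true, and this subgroup rule does not affect the primary test. But the label limits the claims made from a p-value; it does not correct a shifted estimate or tell the reader about it.

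Second, the size is not known. This stands. The documents give neither the rate nor the spread for this subgroup. The 0.40 corner needs every subject to have the same rate, while SAP 2.3 bases the design on flares being subject specific. At 2-3 flares per year the shift is small. The table also leaves out the 90-day merge: with it, and earlier flares on record, the ratio at 2.0 per year is about 0.90-0.92 rather than 0.93-0.97.

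Third, other forces may push the other way. Older flares may be under-recorded, and Protocol 6.2 allows one earlier TNF antagonist. To cancel the selection effect, a fraction s/o - 1 of the older year's flares would have to be lost: 15-58% at 1.0 per year; at 0.292, 61% for k = 4 and unattainable for k of 2 or less.

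Four stronger readings are tempting and not supported:
- That SAP 8.2.1 plans a biased ratio or test. It plans rates with confidence intervals, and gives no pre-study window for the Week 48 rates.
- That the 48-week models will be run in this subgroup. The documents do not say so.
- That all subjects are selected in the same way. Inclusion criterion 7 reads "Subjects must have a documented history of AU diagnosed by an ophthalmologist and" and then breaks off in the available text, so this cannot be judged.
- That moving the comparator to days -730 to -366 gives an unbiased answer. The year-only dates show otherwise.

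**Conclusion.** The concern holds for the subgroup analysis in SAP 8.1.2 and for the subgroup rates in SAP 8.2.1. With a constant within-subject rate, the selection component favours CZP in every scenario examined. Its size could be large near the planning rate and minor if most subjects flare two or three times a year. The observed ratio also reflects recording and earlier treatment, so a ratio below 1 is neither proof of bias nor, alone, evidence of reduction. Confidence is high for the direction and moderate for the sizes, which rest on assumed rates and spread. This should be fixed, but it does not undermine the trial.

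**What to change.** 1. Keep the planned subgroup analysis. State beside its ratio and rates that the comparator includes the qualifying flare and is expected to favour CZP, and do not present the ratio or nominal p-value alone as evidence of reduction.
2. Add one subgroup sensitivity analysis, with matching rates, using days -730 to -366 for both historical count and offset, in subjects whose first uveitis flare preceded day -730. Use investigator-reported flares, a version SAP 8.1.2 already plans ("The AU flares as reported by the investigators, without programmatically correcting for the 3 month interval between 2 flares"), with merged episodes as a secondary version only.
3. Run it twice, with year-only flares imputed as planned and with them left out, and report how many there are. The two runs bracket the no-effect value. SAP 6.2 also moves partial first-flare dates earlier, which can admit subjects whose first flare fell inside the window; say so.

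The cost is SAP wording, a few model runs and extra table rows; up to two years of flare history are already collected. State these downsides:
- Precision is low. At 0.292 per year the subgroup is 86 × (1-P0), about 15-22 subjects, and simulated power for a true ratio of 0.5 is 25-46%.
- It relies on complete recording 13-24 months back. Losing 25% of those flares would move the no-effect ratio to 1/0.75 = 1.33.
- If flares before day -730 are not recorded and merged episodes are used, the simulated no-effect ratio at 2.0 per year is 0.84-0.95, with false-positive rates up to about 0.37. Hence the preference for unmerged flares.

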8.2 Statistical analysis of the secondary efficacy variable(s)

Secondary and other efficacy variables will be summarized by time point including change from Baseline or shift from Baseline, with descriptive statistics. Arithmetic mean, SD, median, minimum and maximum value will be displayed for continuous variables. The secondary efficacy variables are assessed at Week 48 and Week 96. All efficacy analyses will be based on the SS or FAS as appropriate.

8.2.1 Number of AU flares per 100 patient-years

The number of AU flares per 100 patient-years in subjects with active axSpA and a history of AU will be calculated and the corresponding 95% confidence interval for both pre-study and on-study periods. Similarly, the number of AU flares per 100 patient-years in subjects with active axSpA and at least 1 AU episode within 12 months prior Baseline, and the corresponding 95% confidence interval will be presented. This variable is also supportive of primary efficacy analysis.

8.2.2 Ankylosing spondylitis disease activity score (ASDAS)

The ASDAS consists of a number of assessments which are scored by the subject and physician and multiplied by a proven formula (van der Heijde et al, 2008) as shown below:

- $0.121 \times$ [redacted] (BASDAI Q2 result)
- $0.058 \times$ [redacted] (BASDAI Q6 result)
- $0.110 \times$ Patient's Global Assessment of Disease Activity (PtGADA)
- $0.073 \times$ [redacted] (BASDAI Q3 result)
- $0.579 \times$ (natural logarithm of the (CRP [mg/L] + 1))

[redacted], PtGADA, [redacted] are all assessed on a numerical scale (0 to 10 units) (Lukas et al, 2009).

The sum of these weighted components gives the ASDAS.

If 1 component for the ASDAS is missing at a given visit, that component will be imputed by carrying the last observation forward, and the ASDAS will be calculated accordingly. If more than one component for the ASDAS is missing, ASDAS will be treated as missing.

For CRP values below the lower limit of quantification ($<4\text{mg/L}$), half the lower limit (2mg/L) will be used as the imputed value. This approach will be used for summaries of CRP as well.

The nomenclature of disease activity was updated by ASAS (Machado et al, 2018). The state 'Moderate Disease Activity' was replaced by 'Low Disease Activity' state. Disease activity categories based on ASDAS are as follows:

- ASDAS-Inactive Disease (ASDAS-ID): $\text{ASDAS} < 1.3$
- ASDAS-Low Disease Activity (ASDAS-LD): $\text{ASDAS} \geq 1.3, < 2.1$
- ASDAS-High Disease Activity (ASDAS-HD): $\text{ASDAS} \geq 2.1, \leq 3.5$
- ASDAS-very High Disease Activity (ASDAS-vHD): $\text{ASDAS} > 3.5$

The variables related to ASDAS clinical improvement are defined as follows:

- ASDAS-Clinically Important Improvement (ASDAS-CII): ASDAS reduction (improvement) of ≥ 1.1 relative to Baseline
- ASDAS-Major Improvement (ASDAS-MI): ASDAS reduction (improvement) of ≥ 2.0 relative to Baseline.

Change from Baseline in ASDAS at Week 48 and Week 96 are secondary efficacy variables.

8.2.3 Bath ankylosing spondylitis disease activity index (BASDAI)

The BASDAI is the most commonly used instrument to measure the disease activity of ankylosing spondylitis. The BASDAI is a validated self-reported instrument which consists of 6 horizontal Numeric Rating Scales (NRSs), each with 10 units to measure the severity of the 5 major symptoms:

over the last week. To give each symptom equal weighting, the average of the 2 scores relating to is taken. The resulting 0 to 50 sum score is divided by 5 to give a final BASDAI score between 0 and 10, with lower scores indicating lower disease activity. The BASDAI questions can be found in appendix 16.4 of the clinical study protocol.

If 1 of the 2 measurements (ie, questions: and) is missing, the other one will be used for the calculation. The same imputation is also applied for the calculation of the ASAS inflammation component, which is calculated as the average of the 2 measurements.

If 1 major symptom of the BASDAI is missing, the sum score of the remaining symptoms will be divided by the number of symptoms assessed. If more than 1 major symptom is missing, the sum score will be set to missing.

A response variable called BASDAI50 is defined as an improvement of at least 50% in the BASDAI compared to Baseline.

Change from Baseline in BASDAI at Week 48 and Week 96 are secondary efficacy endpoints.

8.2.4 ASAS20, ASAS40, and ASAS PR

The ASAS20 response is defined as an improvement of at least 20% and absolute improvement of at least 1 unit on a 0 to 10 NRS in at least 3 of the 4 following domains (Anderson, 2001):

- Patient's Global Assessment of Disease Activity;
- Pain assessment (the total spinal pain NRS score);
- Function (represented by the Bath Ankylosing Spondylitis Functional Index (BASFI));
- Inflammation (the mean of the Bath Ankylosing Spondylitis Disease Activity Index (BASDAI) questions [Q] 5 and 6) [REDACTED]

and absence of deterioration in the potential remaining domain [deterioration is defined as a relative worsening of at least 20% and an absolute worsening of at least 1 unit].

The ASAS criteria for 40% improvement are defined as relative improvement of at least 40% and absolute improvement of at least 2 units on a 0 to 10 NRS in at least 3 of the 4 domains and no worsening at all in the remaining domain.

The ASAS partial remission (PR) response is defined as a score of ≤ 2 units on a 0 to 10 unit scale in all 4 domains.

